3.4.1.2 Rescue Medications & Supportive Care Guidelines

Subjects should receive appropriate supportive care measures as deemed necessary by the treating Investigator. Suggested supportive care measures for the management of AEs with potential immunologic etiology are outlined below. These treatment guidelines are intended to be applied when the Investigator determines the events to be related to the APX005M and nivolumab combination and should not substitute for investigational product dose delays and/or modifications (Section 3.7). Additional guidance for management of AEs with potential immunologic etiology is provided in the APX005M and nivolumab Investigator's Brochures.

If after evaluation the event is determined by the Investigator not to be related, the Investigator does not need to follow the treatment guidance outlined in this section.

For each disorder, attempts should be made to rule out other causes such as metastatic disease, or bacterial/viral infection, which might require additional supportive care.

Steroid tapering may be necessary for prolonged exposures to corticosteroids, or if symptoms worsen when the corticosteroid dose is decreased.

- **Diarrhea/Colitis**

Subjects should be carefully monitored for signs and symptoms of enterocolitis (such as diarrhea, abdominal pain, blood or mucus in stool, with or without fever) and of bowel perforation (such as peritoneal signs and ileus). All subjects who experience diarrhea/colitis should be advised to drink liberal quantities of clear fluids. If sufficient oral fluid intake is not feasible, fluid and electrolytes should be substituted via IV infusion. For Grade 2 or higher diarrhea, consider GI consultation and endoscopy to confirm or rule out colitis.

- **Grade 1-2:** for subjects developing Grade 1–2 diarrhea loperamide (2 mg every 2 hours) is strongly recommended at the first onset of symptoms. For subjects with persistent diarrhea despite the use of loperamide, or Grade 2 colitis, the use of oral corticosteroids is recommended. Other antidiarrheal agents (e.g. octreotide) may be used if necessary.
- **Grade 3-4:** treat with IV corticosteroids followed by oral corticosteroids until symptoms improve to Grade 1 or less. Add prophylactic antibiotics for opportunistic infections and consider lower endoscopy.

- **Creatinine Elevation Due to Inflammatory Causes**

- **Grade 2-3:** treat with IV or oral corticosteroids until symptoms improve to Grade 1 or less. Consider renal biopsy with nephrology consult.
- **Grade 4:** treat with IV corticosteroids followed by oral corticosteroids until symptoms improve to Grade 1 or less. Add prophylactic antibiotics for opportunistic infections. Consider renal biopsy and consult nephrologist.

- **Pneumonitis**

- **Grade 2:** request pulmonary and infectious disease consults. Treat with IV or oral corticosteroids until symptoms improve to Grade 1 or less. Consider bronchoscopy, lung biopsy and hospitalization.
- **Grade 3-4:** request pulmonary and infectious disease consults. Hospitalize and treat immediately with IV corticosteroids. Administer additional anti-inflammatory measures, as needed. Add prophylactic antibiotics for opportunistic infections. Consider bronchoscopy and lung biopsy.
- **Liver Function Tests**
 - **Grade 2:** monitor liver function tests more frequently until returned to Grade 1 or less. If no improvement in 5-7 days, treat with IV or oral corticosteroids until symptoms improve to Grade 1 or less.
 - **Grade 3 and 4:** treat with IV corticosteroids for 24-48 hours followed by oral corticosteroids until symptoms improve to Grade 1 or less. If no improvement in 3-5 days administer additional immunosuppressive measures (e.g. mycophenolate mofetil), as needed. Add prophylactic antibiotics for opportunistic infections. Consult gastroenterologist.
- **Endocrinopathy**
 - **Asymptomatic TSH abnormality:** monitor fT4 if TSH is $<0.5 \times \text{LLN}$, $> 2 \times \text{ULN}$ or consistently out of range in two subsequent measurements. Consider endocrinology consult.
 - **Symptomatic endocrinopathy:** evaluate endocrine function and consider a pituitary scan. For abnormal laboratory results/pituitary scan initiate IV corticosteroids followed by oral or IV corticosteroids until symptoms improve to Grade 1 or less. Initiate appropriate hormone therapy. For normal laboratory results/pituitary scan repeat labs in 1-3 weeks and pituitary scan in 1 month.
 - **Suspicion of adrenal crisis:** rule out sepsis, administer IV fluids. Consult endocrinologist and if adrenal crisis is ruled out, treat as for symptomatic endocrinopathy. Otherwise, administer stress dose of IV steroids with mineralocorticoid activity.
- **Skin Adverse Events**
 - **Grade 1-2:** symptomatic treatment (e.g. antihistamines, topical steroids). For persistent ($>1-2$ weeks) or recurrent symptoms consider skin biopsy and treatment delay.
 - **Grade 3-4:** consider skin biopsy and consult dermatologist. Treat with IV corticosteroids followed by oral corticosteroids until symptoms improve to Grade 1 or less.
- **Infusion Reaction/Cytokine Release Syndrome**

Precautions should be observed during the administration of APX005M and nivolumab. Emergency agents including oxygen, oral and endotracheal airways, intubation equipment epinephrine, antihistamines, and corticosteroids should be available and used if required at the Investigator's discretion.

Subjects should be instructed that symptoms associated with cytokine release syndrome/infusion reaction can occur within 48 hours following the administration of the APX005M or nivolumab, and if such symptoms develop while they are at home, they should contact the Investigator and/or seek emergency medical care if appropriate.

- **Grade 2:** stop infusion and treat symptoms following guidance in [Table 3](#). If symptoms resolve within two hours, the infusion may be restarted at 50% of the original infusion rate (e.g., from 100 mL/hr to 50 mL/hr).
- **Grade 3-4:** stop infusion and treat symptoms following guidance in [Table 3](#).

Table 3: Guidance for Management of Cytokine Release/Infusion Reaction Symptoms

Suspected Cytokine Release/Infusion-related Toxicity		Recommended Treatment

 Mild toxicity requiring symptomatic treatment only (e.g., fever, nausea, fatigue, headache, myalgia, malaise) 		
 Vigilant supportive care Maintain adequate hydration Antipyretics, non-steroidal anti-inflammatory drugs, antihistaminics, anti-emetics, analgesics as needed In case of mild symptoms persisting for > 48 hours assess for infections; empiric treatment of concurrent bacterial infections

 Symptoms or clinical findings requiring and responding to moderate intervention, such as: 
 O₂ requirement < 40% Hypotension responsive to fluids ± low dose of one vasopressor (e.g., < 50 mg/min phenylephrine) CTCAE Grade 2 organ toxicity 	
 No extensive co-morbidities 	
 All of the above Monitor cardiac and other organ functions closely
	
 Extensive co-morbidities Age ≥ 70 years 	
 All of the above Administer tocilizumab (per ACTEMRA prescribing information) Administer corticosteroids if symptoms worsen or do not improve in <4 hours.

 Symptoms or clinical findings requiring aggressive intervention, such as: 
 O₂ requirement ≥ 40% Hypotension requiring high dose or multiple vasopressors Ventilator support required CTCAE Grade ≥3 organ toxicity 		

- Neurological Toxicity**
 - Grade 2:** symptomatic treatment per local guidelines.
 - Grade 3-4:** obtain neurological consult and treat symptoms per local guidelines. Administer IV corticosteroids followed by oral corticosteroids until symptoms improve to Grade 2 or less. If symptoms worsen or for atypical presentation consider and additional immunosuppressive measures per local guidelines.
- Myocarditis Toxicity**
 - Grade 2:** Hospitalize with cardiac monitoring. Obtain cardiology consult for evaluation and monitoring. Administer IV corticosteroids followed by oral corticosteroids until symptoms improve.

- **Grade 3-4:** Hospitalize to intensive cardiac monitoring. Obtain cardiology consult for evaluation and monitoring. Immediately, administer IV corticosteroid bolus. For Grade 4, transfer to institution with cardiac expertise and consider Antithymocyte Globulin (ATG) as second agent.

3.4.1.3 Permitted Concomitant Medications

All treatments that the Investigator considers necessary for a subject's welfare may be administered at the discretion of the Investigator in keeping with the community standards of medical care. All concomitant medication will be recorded on the electronic case report form (eCRF) including all prescription, over-the-counter, herbal supplements and IV medications and fluids. If changes occur during the Treatment Phase, documentation of drug dosage, frequency, route, and date may also be included on the eCRF.

All concomitant medications received from the time of first dose of investigational product and up to 30 days after the last dose of trial treatment should be recorded.

3.4.1.4 Prohibited and/or Restricted Therapies

Subjects are prohibited from receiving the following therapies during the Screening and Treatment Phase of this trial:

- Antineoplastic systemic chemotherapy or biological therapy
- Investigational agents other than APX005M and nivolumab
- Radiation therapy (radiation therapy to a symptomatic solitary lesion or to the brain may be considered on a case by case basis after consultation with Apexigen Medical Monitor (or designee). The subject must have clear measurable disease outside the radiated field.
- Live vaccines within 30 days prior to the first dose of trial treatment and while participating in the trial. Examples of live vaccines include, but are not limited to, the following: measles, mumps, rubella, chicken pox, yellow fever, rabies, BCG, and typhoid (oral) vaccine. Seasonal influenza vaccines for injection are generally killed virus vaccines and are allowed. However, intranasal influenza vaccines (e.g. Flu - Mist[®]) are live attenuated vaccines and are not allowed.
- Systemic corticosteroids for any purpose other than to modulate symptoms from an event of clinical interest of suspected immunologic etiology. The use of physiologic doses of corticosteroids may be approved after consultation with the Apexigen Medical Monitor (or designee). Inhaled corticosteroids are allowed for management of asthma.
- Medications described in the Exclusion Criteria.

Subjects who, in the assessment by the Investigator, require the use of any of the aforementioned treatments for clinical management may be discontinued from study.

Herbal medicine for anticancer treatment (such as botanical formulation 'Xiao Chai Hu Tang') should be stopped 1 week prior to 1st dose of investigational product.

Subjects taking narrow therapeutic index medications (such as warfarin, phenytoin, quinidine, carbamazepine, phenobarbital, cyclosporine, and digoxin) should be monitored proactively.

There are no prohibited therapies during the Follow-up Phase.

3.5 Dose Limiting Toxicity

All toxicity will be graded according to the NCI-CTCAE version 4.03. DLT will be defined as any of the following events attributed to APX005M and nivolumab combination (e.g., AEs that are not clearly attributable to extraneous causes), and occurring during the first 21-day following the administration of APX005M and nivolumab (the first 3-week cycle):

- Grade 4 hematologic toxicity lasting ≥ 7 days (except asymptomatic lymphopenia)
- Grade 3 or 4 neutropenia with a single temperature of $>38.3^{\circ}\text{C}$ (101°F) or a sustained temperature of $\geq 38^{\circ}\text{C}$ (100.4°F) for more than one hour
- Grade 4 thrombocytopenia (platelet count $<25,000$ cells/ mm^3) or Grade ≥ 3 thrombocytopenia with signs or symptoms of bleeding or requiring platelet transfusion
- Grade 4 non-hematologic toxicity (not laboratory)
- Grade 3 non-hematologic toxicity (not laboratory) lasting >3 days despite optimal supportive care
- Any Grade ≥ 3 non-hematologic laboratory value if:
 - Medical intervention is required to treat the subject, or
 - The abnormality leads to hospitalization, or
 - The abnormality persists for >1 week
- Failure to recover from a treatment-related AE to baseline or \leq Grade 1 within 12 weeks of last dose of investigational product (except Grade 2 alopecia and Grade 2 fatigue)
- Grade 5 toxicity.

3.6 Retreatment Criteria

Subjects that do not meet any of the criteria for treatment discontinuation ([Section 4.1](#)) may start a new cycle of APX005M and nivolumab as scheduled if WBC $>1,500/\text{mm}^3$, ANC $>1,000/\text{mm}^3$, platelets $>100,000/\text{mm}^3$, hemoglobin ≥ 8 g/dL, and disease or treatment-related AE has resolved to baseline or \leq Grade 1 (excluding Grade 2 alopecia and Grade 2 fatigue).

Subjects who have experienced a \leq Grade 2 skin suspected adverse reaction may resume treatment in the presence of Grade 2 skin toxicity.

Drug-related pulmonary toxicity, diarrhea or colitis must have resolved to baseline before treatment is resumed. Subjects with persistent Grade 1 pneumonitis after completion of a steroid taper over at least 1 month may be eligible for retreatment if discussed with and approved by Apexigen Medical Monitor (or designee).

For subjects requiring corticosteroid treatment, allow for a minimum of 7 days from last dose before beginning a new cycle.

If a subject fails to meet criteria for retreatment then the treatment cycle should be delayed and the subject should be re-evaluated weekly.

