3.3 Timing of Investigational Products Administration

Investigational products may be administered up to 3 days before or after the scheduled Day 1 in the case of medical / surgical events or logistical reasons not related to study therapy (e.g., elective surgery, unrelated medical events, patient vacation, and/or holidays); if retreatment criteria are met subjects should restart treatment within 12 weeks of last dose of investigational product unless otherwise discussed with Apexigen (or designee). Every effort should be made to maintain a 21-day dosing schedule. The reason for delay will be documented in the patient's study record.

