3.7 Dose Modifications

Suspected adverse reactions (SAR) (for definition see [Section 6.1.2](#)) associated with APX005M and nivolumab exposure may represent an immunologic etiology. These AEs may occur shortly after the administration of investigational products or several months after the last dose of investigational product. Management of suspected adverse drug reactions may require treatment hold, dose reduction of APX005M, or discontinuation of one of both investigational products as per [Table 4](#). If a subject experiences several toxicities, the recommended dose modification should be based on the highest grade toxicity.

See [Section 3.4.1.2](#) for supportive care guidelines, including use of corticosteroids.

Table 4: Dose Modification Guidelines for Suspected Adverse Reactions

Toxicity	Grade	APX005M	Nivolumab
Neutropenia (± febrile)	3-4	Hold	Hold
Thrombocytopenia	3	Hold. Dose reduction if > 7 days	Hold
	4	Hold. Dose reduction	Hold. Discontinue if > 7 days
	3-4 with bleeding	Discontinue	Discontinue
Diarrhea/colitis	2	1 st occurrence: hold 2 nd occurrence: dose reduction	Hold
	3	1 st occurrence: dose reduction 2 nd occurrence: discontinue	Discontinue
	4	Discontinue	Discontinue
Uveitis, eye pain or blurred vision that does not improve to Grade 1 before next cycle	2-4	Hold	Discontinue
Increased bilirubin	2	Hold	Hold
	3-4	Discontinue	Discontinue
Increased AST, ALT	2	Hold	Hold
	3	Hold. Dose reduction For subjects with liver metastasis reduce dose only if Grade 3 > 72 hours	Discontinue
	4	Discontinue	Discontinue
Endocrinopathies	2	Hold	Hold
	3-4	1 st occurrence: Hold. Institute endocrine replacement therapy 2 nd occurrence: discontinue after consultation with Medical Monitor	1 st occurrence: Hold. Institute endocrine replacement therapy* 2 nd occurrence: discontinue after consultation with Medical Monitor
Nivolumab infusion reaction	2	Administer additional premedication. Increase infusion time to 90 min	1 st occurrence: continue 2 nd occurrence: discontinue
	3	Hold for 1 cycle. Continue single agent at following cycle	Discontinue
	4	Discontinue	Discontinue

Toxicity	Grade	APX005M	Nivolumab
APX005M infusion reaction/cytokine release syndrome	3	Hold. Dose reduction	Hold
	4	Discontinue	Discontinue
Pneumonitis	2	1st occurrence: hold 2nd occurrence: discontinue	1st occurrence: hold 2nd occurrence or if > 14 days: discontinue
	3-4	Discontinue	Discontinue
Creatinine elevation	2	Hold	Hold. Discontinue if > 7 days
	3	Hold	Hold. Discontinue if > 7 days

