	4	Discontinue	Discontinue
Rash or other skin toxicity	2	Hold	Continue. Hold if > 7- 14 days
	3	Hold	Hold
	4	Discontinue	Discontinue
Neurological toxicity	2	Continue	Hold
	3-4	Hold	Discontinue
Hypotension, severe dehydration, shock out of proportion to current illness or suspected adrenal crisis	3	Hold. Dose reduction	Hold
	4	Discontinue	Discontinue
Fatigue	2 >6 weeks 3	Dose reduction	Grade 2: continue Grade 3: hold
Myocarditis	2	Hold	Hold
	3-4	Discontinue	Discontinue
All other drug-related non-hematologic toxicity	3 or Severe	1st occurrence: hold 2nd occurrence: dose reduction	Hold
	4	Discontinue [#]	Discontinue [#]
Hold = hold until retreatment criteria are met (Section 3.6) Dose reduction = reduce dose by one dose level in following cycle (Section 3.7) Discontinue = permanently discontinue that investigational product * Adrenal insufficiency requires discontinuation of nivolumab regardless of control with hormone replacement # Subjects may continue treatment for transient Grade 4 toxicity (such as electrolyte imbalances ≤ 72h, amylase or lipase increase) not associated with clinical sequelae after discussion with the Apexigen Medical Monitor (or designee).			

Dose reductions for APX005M are defined in [Table 5](#). Subjects requiring more than 2 dose reductions or a dose reduction below DL1, must discontinue APX005M.

Table 5: Modified DLs for APX005M Following Qualifying Suspected Adverse Reactions

Dose Level (mg/kg)	DL1 (0.03)	DL2 (0.1)	DL2a (0.2)	DL3 (0.3)
First Dose Reduction	Discontinue	0.06	0.1	0.2
Second Dose Reduction	Not applicable	0.03	0.06	0.1

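### The 7-day corticosteroid washout in Protocol Section 3.6 exempts no physiologic replacement dose and so, read literally, conflicts with the text that lets the Medical Monitor approve such doses

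*Protocol*

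**What the plan says.** Section 3.6 lists what a subject must satisfy before a new cycle of APX005M and nivolumab. One item reads: "For subjects requiring corticosteroid treatment, allow for a minimum of 7 days from last dose before beginning a new cycle". The section closes with the consequence of failing any item: "If a subject fails to meet criteria for retreatment then the treatment cycle should be delayed and the subject should be re-evaluated weekly".

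Other parts of the protocol deal with low-dose or replacement steroid differently:

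- **Section 2.2.1.2, exclusion 4** bars systemic corticosteroids in the 28 days before first dose, but lets the Medical Monitor approve physiologic doses.
- **Section 2.2.1.2, exclusion 12** gives hormone replacement after adrenal crisis as an example of a history that does not exclude a melanoma subject.
- **Section 3.4.1.4** repeats the physiologic-dose permission for the Screening and Treatment Phase.
- **Section 4.1** makes steroid use a reason to stop treatment only if it cannot be reduced to 10 mg/day or less of prednisone equivalent within 12 weeks of the last dose of investigational product.
- **Section 3.7, Table 4** answers a first Grade 3-4 endocrinopathy with "Hold. Institute endocrine replacement therapy" for both drugs. The legend adds "Hold = hold until retreatment criteria are met", and a footnote adds "Adrenal insufficiency requires discontinuation of nivolumab regardless of control with hormone replacement".

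The SAP repeats the exclusion and withdrawal criteria (Sections 2.3.2.3 and 2.3.3) but not the retreatment criteria, so it does not settle the matter.

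**The concern.** A subject taking replacement steroid every day never has 7 days since the last dose. If the sentence means what it says, a subject whom the Medical Monitor has approved for the trial, on that very medication, can be given Cycle 1 and then fails the retreatment criteria at every later visit. Section 4.1 would not take the subject off treatment for the steroid either, provided the dose is at or below its threshold. The subject would be neither discontinued nor eligible for dosing.

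Consistent dosing is at stake. One site may apply the sentence as written and withhold cycles; another may read it as covering only steroid courses for adverse events and dose on schedule. The Synopsis plans about 15 to 20 sites.

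**Working it through.** The plan gives no figure on this point, so the check is mainly a comparison of texts.

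**Step 1: scope of the rule.** Section 3.6 applies to subjects who require corticosteroid treatment. It does not say for what purpose or at what dose. The same section does write out its other exceptions: Grade 2 alopecia and fatigue, Grade 2 skin toxicity, and persistent Grade 1 pneumonitis after a taper, the last with Medical Monitor approval. The steroid sentence has no exception and no approval clause.

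**Step 2: the permissions.** Exclusion 4 and Section 3.4.1.4 allow approved physiologic doses before and during treatment. They lift an exclusion and a prohibition. Neither mentions the retreatment criteria, so neither expressly waives the 7-day condition.

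**Step 3: the timing rule.** Section 3.3 says "if retreatment criteria are met subjects should restart treatment within 12 weeks of last dose of investigational product unless otherwise discussed with Apexigen". The room for discussion concerns the 12-week limit and presupposes that the criteria are already met. It does not help a subject who cannot meet them.

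**Step 4: the discontinuation rule.** Section 4.1 sets a threshold of 10 mg/day, not zero. That fits a plan in which low-dose steroid can coexist with treatment, and sits badly with a retreatment rule that demands 7 steroid-free days.

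**Step 5: the schedule for one subject under the literal rule.** Inputs are the 21-day cycle, the weekly re-evaluation (Section 3.6) and the 12-week restart limit (Section 3.3).

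- Later cycles due after Day 1: 1 + 21 = 22, then 43, 64 and 85.
- Twelve weeks after Day 1: 1 + 84 = Day 85, so 4 later cycles fall due by the limit.
- Weekly re-evaluations from Day 22 to Day 85: (85 − 22)/7 + 1 = 10.
- Continuous replacement never gives 7 days since the last dose, so 0 of 10 re-evaluations pass and 0 of 4 cycles start.
- With an exemption, up to 4 of 4 could start, if every other criterion is met on time.

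These counts only spell out the literal rule over the protocol's calendar. They do not measure how often it would bite.

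**Step 6: the Table 4 route.** For a first Grade 3-4 endocrinopathy APX005M is held, and a hold ends when Section 3.6 is satisfied. The footnote on adrenal insufficiency stops nivolumab only. One can infer that APX005M was meant to be able to restart on replacement. The inference has three limits. Table 4 says only that the drug is held. The steroid rule matters only in adrenal or pituitary cases, since other endocrine replacement, such as thyroid hormone, is not a corticosteroid. Section 3.6 also requires the event to have returned to baseline or Grade 1 or less, and the protocol does not say how controlled adrenal insufficiency would be graded. This route is supporting evidence only.

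**The case against.** The best reply is that the sentence presupposes a finite course. It counts from a last dose, follows directly on the pneumonitis taper, and uses the vocabulary that Section 3.4.1.2 uses for treating adverse events. Replacement has its own terms elsewhere. Approval under Section 3.4.1.4 would have little purpose if it blocked every later cycle, so the specific permission can sensibly be taken to govern. The Medical Monitor also approves each subject for enrolment (Section 3.1) and is consulted on each physiologic dose, which gives a natural occasion to settle cycle timing.

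Much of this stands. It shows the probable intent and limits how far sites would diverge. It does not remove the conflict, because the intent is nowhere stated and Section 3.6 spells out its other exceptions.

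Three stronger readings are tempting and are not supported:

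- **That the protocol makes sites stop replacement for 7 days before each cycle.** It does not. Section 3.6 prescribes delay and re-evaluation, Section 3.4.1.2 directs hormone therapy and stress-dose steroids where indicated, and Section 3.4.1.3 permits treatment needed for the subject's welfare.
- **That Table 4 orders APX005M to resume once replacement starts.** It says only that the drug is held; resumption is inferred, with the limits given in Step 6.
- **That the trial's inference is affected.** Nothing in the Simon design, its decision rules or the ORR analysis depends on this sentence.

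**Conclusion.** The point holds as a conflict between stated rules: wrong as written, low impact. Applied literally, Section 3.6 bars every cycle after the first for a subject on continuous physiologic steroid whom exclusion 4 and Section 3.4.1.4 allow to be treated, and it fits poorly with the Section 4.1 threshold. The conflict does not depend on Table 4.

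The conclusion assumes that replacement is continuous, that the dose is within the Section 4.1 threshold, and that a site applies the sentence without an unwritten exemption. If sites already exempt replacement, the effect is nil. The documents give no count of such subjects; it is likely small. There is no effect on sample size, error rates or the primary analysis.

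**What to change.** Amend the one sentence in Protocol Section 3.6. After the opening phrase that identifies subjects requiring corticosteroids, insert: *except Medical Monitor-approved physiologic replacement doses*. Keep the 7-day minimum for everyone else. Then add: *Replacement must not be interrupted to meet this criterion.* The added sentence closes off the unsafe way of complying, although the protocol does not call for it.

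The change removes only the steroid barrier. A subject held under Table 4 would still have to meet the other retreatment criteria, including resolution of the event.

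The cost is one edited sentence and one new one. The SAP needs no change, and no procedures, visits or subjects are added.
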